2 SAMPLE SIZE DETERMINATION

It is anticipated that approximately 72 patients (67 to 77 patients) will be enrolled in this study (Dose Escalation and Expansion Parts).

Dose Escalation Part

It is anticipated that approximately 30 to 40 DLT-evaluable patients will be entered in the Dose Escalation Part. The actual sample size will vary depending on DLTs observed and number of dose levels actually explored.

Any patient who is not evaluable for DLT, ie, who discontinues the study treatment before the end of Cycle 1 for any reason other than DLT, or who did not receive treatment as planned, will be replaced.

Expansion Part

It is hypothesized that SAR440234 would induce a response rate of 40% and that the null hypothesis for ORR is 20%. Under these hypotheses and using a Simon 2-stage design (optimal), with a 1-sided 10% significance level and a power of 90%, it is planned to enroll 37 patients in the Expansion Part of the study. Eleven (11) responses out of 37 patients will be necessary to reject the null hypothesis (H_0 response rate = 20%).

An interim analysis of the ORR will be done after treatment of the first 17 patients through 2 cycles. If 3 or fewer responses (CR, CRI, or PR) are observed, the Expansion Part will be stopped due to futility.

3 ANALYSIS POPULATIONS

The following populations for analyses are defined:

Table 3 - Populations for analyses

Population	Description
Screened	All participants who have given their informed consent.
All-treated	All participants from the screened population and exposed to the investigational drug, regardless of the amount of treatment administered.
Efficacy	All participants from the all-treated population with at least one post-baseline evaluable disease assessment allowing status evaluation.
DLT-evaluable	All participants in the dose escalation part, who have received at least 5 out of 6, weekly IV administrations of SAR440234 in DL1 and DL2, or at least 6 out of 7 IV administrations of SAR440234 in DL \geq 3. Patients who discontinue the IMP before completion of Cycle 1 because of a DLT will also be included in the DLT-evaluable population. Patient who discontinues the study treatment before the end of Cycle 1 for another reason than DLT will be replaced.
Pharmacokinetic (PK)	All participants from the all-treated population with at least one drug concentration post-baseline (whatever the cycle and even if dosing is incomplete).
ADA	All participants from the all-treated population with at least 1 available ADA result (positive, negative or inconclusive) post-baseline.
Biomarker	All participants from exposed population with at least one valid assessment for: 
• CRP or ferritin, or• Cytokines, or• Disease molecular subtype, or• immunophenotyping by flow cytometry, or• MRD.

For any participant enrolled and treated more than once, only the data associated with the first enrollment will be used in any analysis population. The safety experience associated with any later enrollment will be reported separately.

4 STATISTICAL ANALYSES

4.1 GENERAL CONSIDERATIONS

In general, continuous data will be summarized using the number of observations available, mean, standard deviation, median, minimum, and maximum. Categorical and ordinal data will be summarized using the count and percentage of participants.

The baseline value is defined as the last available value before the first administration of SAR440234. For participants enrolled but not treated, the baseline value is defined as the last available value before enrollment.

Unless otherwise specified, analyses will be performed by part, by dose level (if applicable) and overall (if applicable).

All efficacy analyses will be performed on the efficacy population. Objective response rate, as well as all other efficacy variables will be derived using the Investigator's assessment.

All safety analyses will be performed on the all-treated population.

Analysis period

The analysis period will be divided into 3 segments:

- The **pre-treatment period** is defined as the period from when the participants give informed consent up to first administration of IMP.
- The **on-treatment period** (ie, treatment-emergent (TE) period) is defined as the period from the first IMP administration to the last IMP administration + 30 days.
- The **post-treatment period** is defined as the period from the end of the on-treatment period, ie, 31 days after the last administration of IMP.

4.2 PARTICIPANT DISPOSITIONS

The number (%) of participants included in each of the analysis populations listed in [Table 3](#) will be summarized.

Screen failures are defined as participants who consent to participate in the clinical study but are not subsequently enrolled. The number (%) of screen failures and reasons for screen failures will be provided in the screened population.

Permanent intervention discontinuation is defined as the discontinuation of SAR440234.

The number (%) of participants in the following categories will be provided:

- Exposed participants
- Participants who did not complete the study period and main reason for study discontinuation.

In addition, the number (%) of participants screened, screened-failed, enrolled, with permanent intervention discontinuation will be provided by country and site.

Protocol deviations

Critical and major protocol deviations (automatic or manual) will be summarized in the enrolled population.

4.3 PRIMARY ENDPOINT(S) ANALYSIS

No primary efficacy endpoint will be analyzed due to early termination of the clinical trial. Primary safety endpoints analyses are defined in [Section 4.7](#).

4.4 SECONDARY ENDPOINT(S) ANALYSIS

No secondary efficacy endpoint will be analyzed due to early termination of the clinical trial. Other secondary endpoints analyses are defined in [Section 4.7](#) (safety), [Section 4.8.1](#) (PK) and [Section 4.8.2](#) (immunogenicity).

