- IMP-related adverse reaction (unless caused by disease progression or an obviously unrelated cause) lasting more than 2 weeks with failure to recover to baseline or improve to Grade <1.

During the Dose Escalation Part, escalation to the next dose level cohort will occur after the last patient has completed the DLT observation period for the previous dose level. Within a dose level, subsequent patients will initiate treatment at least 1 week after the first patient in that dose level started treatment with SAR440234.

The occurrence of DLTs will inform the dose recommendation that will be used during the Expansion Part.

Response will be evaluated by a bone marrow aspirate at the end of Cycle 1 (Day 42 ±2 days). Patients may continue treatment with the IMP as long as clinical benefit is possible, or until disease progression, unacceptable adverse reaction, patient's decision to stop the treatment, or other reason for discontinuation (Section 6.5). Bone marrow aspirate will be performed on Day 42 (±2 days) of Cycle 2. Additional bone marrow aspirate is required if onset of cytopenia >14 days before or after Day 42. Subsequent bone marrow aspirates will be performed when clinically indicated, as determined by the treating physician. Additional bone marrow aspirate shall be performed as clinically indicated or if any of the following occurs: if decreased neutrophil count Grade 4, decreased platelet count Grade 4, febrile neutropenia Grade 3 and Grade 4, or anemia Grade 4 occurs with onset in >14 days before or after Day 42.

Response assessment will be performed according to the International Working Group (IWG) 2003 recommendations for AML (19) and the revised 2000 criteria for HR-MDS (34), and the 2016 National Comprehensive Cancer Network (NCCN) Guidelines for ALL (Appendix D, Appendix F, and Appendix H).

If at the end of a cycle the patient exhibits clinical benefit by symptoms or response criteria and does not meet study treatment discontinuation criteria, the patient may continue therapy until an unacceptable AE, disease progression, patient's decision to stop the treatment, or any other reason.

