Secondary	
 To characterize the safety profile of SAR440234 including cumulative adverse drug reactions. To characterize the pharmacokinetic profile of SAR440234 when administered as a single agent. To evaluate the potential immunogenicity of SAR440234. To assess any preliminary evidence of hematologic response in the Dose Escalation Part. 
 The safety profile of SAR440234 in terms of treatment-emergent adverse events (TEAEs), serious adverse events (SAEs), and changes in laboratory parameters, vital signs, electrocardiograms (ECGs), and assessment of physical examination. Pharmacokinetic parameters of SAR440234: Concentration observed at the end of IV infusion, maximum concentration observed (Cmax), time to reach Cmax, last concentration observed above the lower limit of quantification, time of the last concentration observed above the lower limit of quantification (ie, Clast), concentration observed just before treatment administration during repeated dosing, area under the plasma concentration versus time curve (area under the curve (AUC)) calculated using the trapezoidal method from time zero to Clast, AUC calculated using the trapezoidal method from time zero to infinity, AUC calculated using the trapezoidal method over the dosing interval (7 days). Incidence rate of anti-drug antibody (ADA, ie, anti-SAR440234 antibody) development. In the Dose Escalation Part, preliminary anti-leukemia activity as defined by IWG for MDS or AML, or NCCN for B-ALL.

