4.9 INTERIM ANALYSES

Not applicable due to early termination of the clinical trial.

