5.2 APPENDIX 2: CHANGES TO PROTOCOL-PLANNED ANALYSES

Not applicable.

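### SAP 4.4 drops the Dose Escalation response endpoint for early termination, a reason that does not reach a descriptive endpoint, and Appendix 2 records no change

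*SAP*

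**What the plan says.** **The endpoint.** Protocol 5.2 makes evidence of hematologic response in the Dose Escalation Part a secondary objective. SAP 1.2 (Table 2) carries the endpoint forward: "In the Dose Escalation Part, preliminary anti-leukemia activity as defined by IWG for MDS or AML, or NCCN for B-ALL".

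**The data the protocol required.** Protocol 6.2.1: "Response will be evaluated by a bone marrow aspirate at the end of Cycle 1". The same section requires a second aspirate at the end of Cycle 2. Protocol 6.8.1 brings the Day 42 evaluation forward to the day of the decision if a patient stops before then.

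**What the SAP keeps.** Table 3 defines an Efficacy population of treated patients with an evaluable disease assessment after baseline. SAP 4.1 adds "All efficacy analyses will be performed on the efficacy population", using the Investigator's assessment of response.

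**What the SAP removes.** SAP 4.3: "No primary efficacy endpoint will be analyzed due to early termination of the clinical trial". SAP 4.4: "No secondary efficacy endpoint will be analyzed due to early termination of the clinical trial". SAP 4.9, on the interim: "Not applicable due to early termination of the clinical trial".

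**What the SAP records as changed.** The whole content of the section headed "5.2 APPENDIX 2: CHANGES TO PROTOCOL-PLANNED ANALYSES" is "Not applicable".

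**The concern.** A single reason, early termination, is used for three different things. It fits the Expansion Part's primary efficacy endpoint and its interim, which need patients whom a stopped trial will not enroll. It does not by itself fit response in the Dose Escalation Part, where each treated patient's response stands alone and no target number is set.

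At stake is a stated secondary objective of a first-in-human trial. As planned, the report would give no response result for patients who were scheduled for marrow procedures partly for that purpose. In addition, a reader who goes to Appendix 2 to see how the analysis departs from the protocol finds no entry.

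**Working it through.** **Step 1. Reproduce the only efficacy design figure.** Inputs from protocol 13.1.2 and SAP 2: stop at 3 or fewer responses in 17; reject at 11 or more in 37; response rates 20% and 40%; one-sided alpha 10%; power 90%. The second stage has 37 − 17 = 20 patients.

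P(reject | p) = Σ over x = 4 to 17 of P(Bin(17, p) = x) × P(Bin(20, p) ≥ 11 − x)

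- p = 0.20: 0.0948, within the 10% allowed.
- p = 0.40: 0.9033, meeting 90%.
- Stopping at the interim under 20%: P(Bin(17, 0.20) ≤ 3) = 0.549.
- Expected size under 20%: 17 + (1 − 0.549) × 20 = 26.0.

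A grid search returns the same optimal design. The figure is sound, and it belongs to the Expansion Part. Without those patients the test cannot be run, so SAP 4.3 and 4.9 follow.

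**Step 2. Ask what the Dose Escalation endpoint needs.** The documents give it no null value, power or sample size. A listing needs one evaluable patient. A proportion can also be computed at any n, with low precision at small n. The number evaluable is not given, so I assume 3 (the patients the protocol says were already treated) to 40 (the upper planned number). With no responses, the upper 95% Clopper-Pearson limit is 1 − 0.025^(1/n):

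| n evaluable (assumed) | Upper limit for 0 responses |
|---|---|
| 3 | 70.8% |
| 6 | 45.9% |
| 10 | 30.8% |
| 20 | 16.8% |
| 40 | 8.8% |

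These are illustrations, not results. Small numbers favor a listing over a rate; they do not favor silence.

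**Step 3. Check the SAP against itself.** SAP 4.2 will report how many patients fall in each Table 3 population, including Efficacy. SAP Appendix 3 will list each patient's best response to the last prior regimen. No section plans any output of response to SAR440234. The report would show how many patients could be assessed, and how they did on their previous treatment, but not how they did on study drug.

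**Step 4. Set the protocol beside the SAP for Appendix 2.**

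| Analysis | Protocol | SAP body |
|---|---|---|
| Primary efficacy (Expansion) | 9.7, 13.1.2, 13.4.8 | Not analyzed (4.3) |
| Secondary efficacy (Dose Escalation) | 5.2 and summary endpoints | Not analyzed (4.4) |
| Interim | 6.9, 13.5 | Not applicable (4.9) |
| ADA impact | On efficacy, PK and safety (13.4.4.6.3) | On PK and safety only (4.8.2) |
| Exposure duration | Last − first dose date + 28 days (13.4.2) | Ends the day before the next dose would be due, 7 days on (4.7.1.1) |
| Dose proportionality and accumulation | To be assessed (13.4.5) | Not mentioned (4.8.1) |

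Exposure example, dosing from Day 1 to Day 36 (a 35-day difference): the protocol gives 35 + 28 = 63 days; the SAP gives 35 + 6 + 1 = 42 days. The change is 63 − 42 = 21 days per patient. None of the six rows appears in Appendix 2.

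**The case against.** The strongest reply is that nothing is hidden. SAP 4.3, 4.4 and 4.9 each state the cut and its reason, so Appendix 2 is a missing cross-reference. That stands: a reader might infer that the SAP conceals the changes, and the documents do not support it. The reply covers neither the ADA and exposure changes, which are nowhere called changes, nor the poor fit between the reason and this endpoint.

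Second, the protocol can be read as planning no response rate for the Dose Escalation Part. Its summary places the response rate and interval under the expansion cohort, and 13.4.8 names no part. This also stands, and it is why the remedy is a listing, not an interval. The secondary objective and endpoint themselves name the Dose Escalation Part without ambiguity.

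Third, evaluable data may be few or absent. Appendix K notes that patients may not survive or be well enough to return for Day 42. A reader might infer that marrow response results exist and are being left out. The documents show only that assessments were required, that at least 3 patients were treated, and that marrow immunophenotyping stays in the SAP.

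Fourth, it would be wrong to infer that all response-related information is lost. SAP 4.7.3.1 keeps blasts among the laboratory variables, and SAP 4.8.3 keeps marrow immunophenotyping, including a blast panel. What is missing is the response classification. Likewise, dose proportionality is left unmentioned, not expressly cancelled.

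**Conclusion.** Two points hold. First, SAP 4.4 removes the only secondary efficacy endpoint for a reason that does not reach it, while the SAP keeps the endpoint, its population and its rules. Second, Appendix 2 contradicts SAP 4.3, 4.4 and 4.9.

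The size is one secondary objective without a response result and five unlisted departures, or six if dose proportionality and accumulation are not to be done. No test, safety analysis or MTD decision changes. The effect in patients is unknown.

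The comparison uses the protocol of 29 August 2019, whereas the SAP names the version of 11 July 2019. The protocol's summary of changes lists no specific change to objectives or to Section 13.4, so I assume that the date difference does not explain the departures.

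**What to change.** **(a) Response.** Add a by-patient listing of all treated Dose Escalation patients, with the number evaluable, giving:

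- disease and assigned dose level, flagging the first 3 patients, whose received doses are uncertain;
- marrow blast percentage at baseline and at each assessment actually done;
- hydroxyurea use, since it is allowed in Cycle 1 to control the white count and could affect blasts;
- investigator-assessed best response.

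If no evaluable assessment exists, say so in one sentence in SAP 4.4 instead.

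**(b) Appendix 2.** Replace the present entry with a list of dropped or changed analyses and the reason for each: primary efficacy, secondary efficacy, the interim, ADA impact on efficacy, the exposure-duration definition, and dose proportionality and accumulation if they are not to be done.

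The cost is one listing and a paragraph. No formal analysis and no new data collection are needed.

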4.5 TERTIARY/EXPLORATORY ENDPOINT(S) ANALYSIS

Tertiary endpoints analyses are defined in [Section 4.8.3](#) (biomarkers).

4.6 MULTIPLICITY ISSUES

No formal testing will be performed. Therefore, no multiplicity issues need to be addressed.

4.7 SAFETY ANALYSES

The analysis of the safety variables will be essentially descriptive, and no testing is planned.

4.7.1 Extent of exposure

4.7.1.1 Overall exposure

The dose information will be assessed by the following variables:

- Overall number of cycles started, defined by the number of cycles in which at least one dose of any study interventions is administered.
- Duration of IMP exposure (in weeks) is defined as (Last day of exposure – first day of exposure +1)/7.
 - The first day of exposure is defined as the first administration date with non-zero dose for at least one of the IMP (SAR440234).
 - The last day of exposure is the day before the theoretical date of the next administration (after the last administration), defined as the last administration date + 7 days for SAR440234.

Overall study treatment exposure will be presented in a listing along with the overall number of cycles started.

4.7.1.2 SAR440234 exposure

The dose information will be assessed by the following:

- Cumulative dose for SAR440234 (ng/kg): the cumulative dose is the sum of all doses from cycle 1 day 1 up to treatment discontinuation
- Actual dose intensity (ng/kg/week) for SAR440234:
$$\text{ADI} = \text{Cumulative dose (ng/kg)} / \text{Overall duration of exposure in weeks}$$
- Planned dose intensity (ng/kg/week) for SAR440234:

$$\text{PDI} = \text{Total planned dose (ng/kg)} / \text{Overall duration of exposure in weeks}$$

The total planned dose for SAR440234 will be calculated by the sum of the theoretical planned dose (ie, the intended dose as per CRF) over the duration of treatment.

- The relative dose intensity (RDI, in %) for SAR440234 is defined as

$$\text{Relative Dose Intensity} = \left(\frac{\text{Actual Dose Intensity}}{\text{Planned Dose Intensity}} \right) \times 100$$

It is an indicator of the feasibility of the chosen schedule of administration.

A listing will be provided for cumulative dose, actual dose intensity and relative dose intensity.

Dose or cycle modifications

- Cycle delay: A cycle is deemed to have been delayed if start date of the current cycle – start date of previous cycle >42 days.
- Dose delay: A dose is deemed to have been delayed if the infusion is made >1 day later than the scheduled administration.
- Dose omission: A dose is considered to be omitted if the dose is not administered at the scheduled visit and 1 or more doses are given afterwards.
- Dose interruption: An infusion is considered to be interrupted if the administration is stopped before the infusion is completed, regardless of whether or not the infusion is restarted.
- Dose reduction: a dose is deemed to have been reduced if the dose taken by a patient is lower than 80% of the intended dose.
- Reason for dose reduction.

Dose information variables will be provided in a listing:

- Cycle/day of occurrence
- Dose reduction Y/N
- Dose omission Y/N
- Dose interruption Y/N
- Cycle delay Y/N

4.7.2 Adverse events

General common rules for adverse events

All adverse events (AEs) will be coded to a lower-level term (LLT), preferred term (PT), high-level term (HLT), high-level group term (HLGT), and associated primary system organ class (SOC) using the Medical Dictionary for Regulatory Activities (MedDRA) version currently in effect at Sanofi at the time of database lock.

The AEs will be analyzed in the following 3 categories:

- Pre-treatment AEs: AEs reported during the pre-treatment period.
- Treatment-emergent adverse events (TEAE)s: AEs that developed, worsened or became serious during the treatment-emergent period
- Post-treatment AEs: AEs that developed, worsened or became serious during the post-treatment period

Similarly, the deaths will be analyzed in the pre-treatment, treatment-emergent and post-treatment periods.

The primary focus of AE reporting will be on TEAEs. Pre-treatment and post-treatment AEs will be described separately.

An AE with incomplete or missing date/time of onset (occurrence, worsening, or becoming serious) will be classified as a TEAE unless there is definitive information to determine it is a pre-treatment or a post-treatment AE.

If the assessment of the relationship to IMP is missing for an AE, this AE will be assumed as related to IMP. If the grade is missing for 1 of the treatment-emergent occurrences of an AE, the grade will be imputed with the maximal severity of the other occurrences. If the grade is missing for all the occurrences, the grade will be left as missing.

Multiple occurrences of the same event in the same participant will be counted only once in the tables within a treatment phase, using the maximum (worst) grade by treatment phase. Summaries will be provided for all grades combined and for grade ≥ 3 (including grade 5). Missing grades, if any, will be included in the “all grades” category.

The AE tables will be sorted as indicated in [Table 4](#).

Table 4 - Sorting of AE tables

AE presentation	Sorting rules
SOC, HLT and PT	By the internationally agreed SOC order and by alphabetic order of HLTs and PTs
SOC and PT	By the internationally agreed SOC order and decreasing frequency of PTs ^{a,b}
PT	By decreasing frequency of PTs ^a

^a Sorting will be based on the AE incidence.

^b The table of all TEAEs presented by SOC and PT will define the presentation order for all other tables (eg, treatment-emergent SAE) presented by SOC and PT, unless otherwise specified.

Analysis of all adverse events

The overview of TEAEs with the details below will be generated:

- Any TEAE
- Any grade ≥ 3 TEAE
- Any treatment emergent SAE
- Treatment related TEAEs (overall and for each individual drug)
- Treatment related TEAEs of Grade ≥ 3 (overall and for each individual drug)
- Serious treatment related TEAEs (overall and for each individual drug)
- Grade 5 TEAE (any TEAE with a fatal outcome during the treatment-emergent period)
- Any TEAE leading to permanent partial intervention discontinuation (for each individual drug)

- Any TEAE leading to permanent full intervention discontinuation

The AE summaries of [Table 5](#) will be generated with number (%) of participants experiencing at least one event. The analyses will be performed for all grades combined and for grades ≥ 3 .

Table 5 - Analyses of adverse events

Type of AE	MedDRA levels
All TEAE	Primary SOC, HLT and PT
TEAE related to IMP (overall and for each drug) as per Investigator's judgment	Primary SOC and PT
Treatment emergent SAE	Primary SOC and PT
Treatment emergent SAE related to IMP (overall and for each drug) as per Investigator's judgment	Primary SOC and PT
TEAE leading to permanent full intervention discontinuation	Primary SOC and PT
TEAE leading to permanent partial intervention discontinuation (for each individual drug)	Primary SOC and PT
TEAE leading to death (death as an outcome of the AE as reported by the Investigator in the AE page)	Primary SOC and PT
Pre-treatment AE	Primary SOC and PT
Post-treatment AE	Primary SOC and PT
TEAE leading to dose interruption	Primary SOC and PT
TEAE leading to dose modification (including dose reduction, dose omission and cycle delay, excluding dose interruption)	Primary SOC and PT

Analysis of deaths

Deaths will be analyzed through a listing with following information:

- Death date
- Study period
- Reason of death
- For AE with fatal outcome: PT, date of onset, relationship

Analysis of adverse events of special interest (AESIs) and other AEs of interest

Adverse events of special interest (AESIs) and other AEs of interest will be selected for analyses as indicated in [Table 6](#). Listings with PT and grade will be provided.

Table 6 - Selections for AESIs and other AEs of interest

AESIs and other AEs of interest	Selection
DLT during cycle 1	e-CRF specific DLT page
Pregnancy of a female participant as well as pregnancy occurring in a female partner of a male participant	e-CRF specific pregnancy page
Symptomatic overdose with IMP/NIMP	e-CRF specific tick box in overdose page
CRS	e-CRF specific category in AE page

Further analyses of Cytokine release syndrome (CRS) with a listing providing a more detailed description of CRS by patient:

- Action taken
- Relationship to IMP according to Investigator's opinion
- Number of episodes
- Onset of first occurrence CRS (at the first infusion and subsequent infusions)
- Day of onset from infusion (by category 1 day/ 2 to 3 days/ More than 3 days when applicable)
- Duration (in days) (by category 1 day/ 2 to 3 days/ More than 3 days)

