# 6.5.3 Dose delay/modification for cytokine release syndrome and infusion-related reactions

Infusion-related reactions and CRS will be graded according to the 2014 NCI Consensus Guidelines (Appendix H). Recovery is defined as resolution to Grade 1 or less. CRS-like symptoms or signs that occur during infusion will be referred to as infusion-related reactions, while CRS-symptoms or signs that develop or persist after the infusion ends will be referred to as CRS. The patient's temperature, heart rate, blood pressure, oxygen saturation, and respiratory rate will be assessed every 30 minutes during the infusion. If clinical signs of an **infusion-related reaction Grade 1** develop, the infusion will be interrupted, and the patient will be treated with acetaminophen, diphenhydramine, and ranitidine, or similar agents. If the reaction remains at Grade 1 or less, the infusion will resume at 50% of the previous rate after up to 60 minutes of interruption. Up-titration of the rate may be attempted according to Section 8.1.2, provided that the AE remains Grade ≤1. If more than 60 minutes of interruption are required, the AE will be treated as for a Grade 2 infusion-related reaction.

If the **infusion-related reaction is Grade** ≥2, interrupt the infusion and treat the reaction. For Grade 2 infusion reactions, if the AE improves to Grade 1 or less within 48 hours, retreatment will be reattempted on the next scheduled day without a dose escalation, following premedication with dexamethasone, montelukast, acetaminophen, diphenhydramine, and ranitidine, or similar agents. If tolerated well, dose escalation (if planned) may resume with the next dose. If the infusion-related reaction persists for >48 hours, it will be managed as for a Grade 3 infusion-related reaction.

For **Grade 3 or Grade 4 infusion-related reactions**, interrupt the infusion and treat the reaction. The next dose will be omitted. After the AE resolves, treatment will restart on the next subsequent scheduled dosing day with additional premedication. Dose reduction by 1 step must be applied (Table 4). Treatment will restart with the lead-in dose.

For CRS Grade 1, no dose modifications or delays are required.

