# Analysis of CRS

The following summaries will be provided:

- Number (%) of patients experiencing CRS (all grades and by grade).
- Number (%) of patients experiencing CRS by action taken with study treatment.
- Number (%) of patients with infusion of occurrence.
- Duration of CRS event (in hours).

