1.2 OBJECTIVE AND ENDPOINTS

Table 2 - Objectives and endpoints

Objectives	Endpoints

Primary
 
• Dose Escalation Part: To determine the maximum tolerated dose (MTD)/maximum administered dose (MAD) of SAR440234 administered as a single agent in patients with R/R AML, HR-MDS, or B-ALL, and determine the recommended phase 2 dose (RP2D) for the subsequent Expansion Part.• Expansion Part: To assess the activity of single agent SAR440234	
• Dose Escalation Part: Incidence of DLT observed during the first 42 days following the first administration of IMP in the first cycle of treatment.• Dose Escalation Part: Incidence of allergic reactions/hypersensitivity and CRS/acute infusion reactions.• Expansion Part: Preliminary anti-leukemia activity as defined by the IWG for MDS or AML: Overall response rate (ORR) including CR, CRI, and partial response, Duration of response, Event-free survival.

Objectives	Endpoints
	at the RP2D in patients with R/R AML, or HR-MDS.

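### SAP 4.7 gives no endpoint-specific or grouped incidence for the second Dose Escalation primary endpoint, and the protocol's CRS counts by grade became a listing with no recorded change

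*SAP*

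**What the plan says.** - **Endpoint.** SAP 1.2, Table 2, keeps as the second primary endpoint: "Dose Escalation Part: Incidence of allergic reactions/hypersensitivity and CRS/acute infusion reactions". Protocol 9.1.1 names the same endpoint and ties it to defining the RP2D and schedule.
- **Where it is analysed.** SAP 4.3 drops the primary efficacy analysis because the trial ended early, then states "Primary safety endpoints analyses are defined in" Section 4.7.
- **Endpoint-specific output.** In SAP 4.7.2, Table 6 selects DLT in Cycle 1, pregnancy, symptomatic overdose and CRS. For these, "Listings with PT and grade will be provided". CRS is identified by "e-CRF specific category in AE page", and its further analysis is planned "with a listing providing a more detailed description of CRS by patient".
- **Generic output.** SAP Table 5 gives n (%) of participants for all TEAEs by SOC, HLT and PT, for all grades and for grade ≥3. Under SAP 4.1 this is done by part, dose level and overall, in the all-treated population.
- **Protocol plan for CRS.** Protocol 13.4.4.2 (Analysis of CRS) plans "Number (%) of patients experiencing CRS (all grades and by grade"), together with n (%) by action taken and by infusion of occurrence, and duration in hours.
- **Labels.** Protocol 6.5.3 says "CRS-like symptoms or signs that occur during infusion will be referred to as infusion-related reactions". It uses CRS for those that arise or continue once the infusion has ended.
- **Record of changes.** SAP Appendix 2, on departures from the protocol's analyses, is entered as not applicable.

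**The concern.** An incidence endpoint needs three things: a rule for which events count, a denominator, and a table that counts each patient once. Section 4.7 supplies none of these for this endpoint as a whole. CRS has a selection rule but only listings. Infusion-related and allergic/hypersensitivity reactions appear in Table 2 and have no selection rule or output of their own after that.

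Acute reactions are the main anticipated risk of this drug class and, by the protocol's own account, inform the RP2D. If the SAP is followed as written, the report will not show what proportion of patients at each dose level had such a reaction, or the CRS counts by grade that the protocol planned. Anyone who wants the grouped figure must choose the terms after the data are in hand.

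**Working it through.** The plan states no figure for this point, so there is nothing to reproduce. The check compares what is declared with what would be produced.

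**1. Early termination.** SAP 4.3, 4.4 and 4.9 cite it for the efficacy endpoints and the interim analysis only. Table 2 keeps the safety endpoint and 4.3 points to its analysis. Early termination is not given as a reason for leaving it out.

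**2. Component by component.**

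| Component | Selected in SAP Table 6 | Dedicated output | Generic output (SAP Table 5) |
|---|---|---|---|
| CRS | Yes, by eCRF category | Listings | n (%) per coded term, all grades and ≥3 |
| Acute infusion reactions | No | None | As above, if coded as a TEAE |
| Allergic/hypersensitivity | No | None | As above, if coded as a TEAE |
| Any of these, per patient | No | None | None |

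**3. Grouping.** Separate term rows do not fix the number of patients with at least one term. Illustration with assumed counts: a dose level of 3 patients, with CRS, infusion-related reaction and hypersensitivity each seen in 1 of 3.
- Fewest patients affected: max(1, 1, 1) = 1, so 1/3 = 33%.
- Most patients affected: min(3, 1 + 1 + 1) = 3, so 3/3 = 100%.

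The same three rows fit anything from 33% to 100%.

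**4. Grade.** SAP Table 5 reports all grades and grade ≥3. The difference between the two mixes Grade 1, Grade 2 and missing grades, because SAP 4.7.2 puts missing grades in the all-grades column. Grades 3, 4 and 5 are merged. A Grade 2 count therefore cannot be read off, although Protocol 6.2.1 makes Grade 2 CRS a DLT under stated conditions of duration or timing.

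**5. Selection.** Table 6 finds CRS through an eCRF category, while Table 5 works from coded terms. The SAP does not say that the two agree, or which one defines the endpoint.

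**6. Timing labels.** Protocol 6.5.3 grades infusion-related reactions and CRS on the same scale and separates them by timing. Protocol 12.1 gives infusions of 1 to 19 hours. If sites applied these labels when completing the CRS category, a reaction that began and resolved during the infusion would not be selected as CRS. One that began during the infusion and continued afterwards would be.

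**7. Departure from the protocol.** The CRS summaries in Protocol 13.4.4.2 are n (%). In the SAP they are listings, and duration moves from hours to days. Appendix 2 shows no change.

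**The case against.** The strongest reply is that SAP 4.3 points to the whole of Section 4.7, not to Table 6 alone. SAP Table 5 counts participants by dose level, with repeats of an event counted once at worst grade, so each coded term for CRS, infusion reaction or hypersensitivity gets an incidence. **This stands.** A reader might infer that the endpoint has no incidence analysis, or is not estimated at all. The documents do not support that: term-level incidences are planned. What is missing is the endpoint-specific and grouped analysis.

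There are also partial routes for infusion reactions. Protocol 6.5.3 calls for interruption of the infusion at every grade of reaction, and SAP Table 5 has a table of TEAEs leading to dose interruption. Some severe reactions in Cycle 1 would also enter the DLT listing. These routes are real, but neither isolates infusion reactions as a group.

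A reader might also infer that the CRS selection misses every on-infusion event. That is not shown. The eCRF is not available, the timing labels sit in a dose-modification section, and Protocol Table 5 on infusion-related reactions itself speaks of CRS. The loss is possible but unquantified.

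Two further points hold in part. The protocol's n (%) plan covers CRS only; its statistical section has no specific analysis of allergic or infusion reactions, so for those the SAP drops nothing. And the endpoint wording can be read as separate incidences rather than one composite. Even so, the separate reading needs a term selection for each component, and the SAP has none beyond CRS.

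Finally, the Study Committee decides escalation from continuing data review (Protocol 6.10), not from these tables. The effect is on reporting. With few patients, CRS counts by grade could be tallied by hand from the listings; reactions with no selection rule or dedicated listing could not be tallied that way.

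**Conclusion.** The point holds in a limited form. SAP 4.7 does not deliver the declared second primary endpoint as a per-patient grouped incidence, or its infusion and hypersensitivity components as defined groups. It also replaces the protocol's CRS n (%) by grade with listings and records no change.

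No numerical size can be given without data. The 33% to 100% range rests on assumed counts and shows only that term rows do not determine the grouped figure. The possible under-selection of on-infusion reactions depends on how sites completed an eCRF category that the documents do not show. The gap is in pre-specification and reporting. It does not show that dose decisions were wrong or that the reactions go unreported.

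**What to change.** 1. Add to SAP 4.7.2 one table in all-treated Dose Escalation patients, by dose level and overall. Give n (%) of patients, each counted once at worst grade, for all grades and by grade, for: (a) CRS; (b) infusion-related reactions; (c) allergic/hypersensitivity reactions, by a prespecified MedDRA term list; (d) any of these. Footnote the grading scale for each row, since Protocol 6.5.3 puts (a) and (b) on the 2014 NCI Consensus scale while other events use NCI-CTCAE v4.03.
2. State whether the CRS eCRF category includes events confined to the infusion.
3. Either restore the CRS n (%) summaries of Protocol 13.4.4.2 or record their replacement by listings in SAP Appendix 2.

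The cost is one extra table, a term list and two short statements. Protocol 10.5.1 already requires all AEs to be recorded. Whether the eCRF has separate categories for infusion or hypersensitivity reactions is not shown, which is why the term list is needed. No clinical rule changes.
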